#### **4.11.2 Secondary Outcome Measures**

a) Change from baseline to all post-treatment visits in body weight [Time Frame: Weeks 0, 2, 4, 12, 24, 36, 48]

Weight in Kg will be recorded for each patient during each follow up

b) Change from baseline to all post-treatment visits in Blood-pressure [Time Frame: Weeks 0, 2, 4, 12, 24, 36, 48]

Blood pressure will be measured in each patient during each follow up

- c) Change from baseline to all post-treatment visits in S.creatinine [Time Frame: Weeks 0, 2, 4, 12, 24, 36, 48]
  - a. S. Creatinine level will be measured during each follow up.
  - b. In case of patients having dialysis Pre and Post dialysis S. Creatinine levels will be measured at or near follow up dates.
- d) Change from baseline to all post-treatment visits in blood urea nitrogen (BUN) [Time Frame: Weeks 0, 2, 4, 12, 24, 36, 48]

Blood Urea Nitrogen will be measured in all patients during each follow up.

- e) Change from baseline to all post-treatment visits in Hemoglobin level [Time Frame: Weeks 0, 2, 4, 12, 24, 36, 48]
  - a. Hemoglobin level will be measured in gm/dl and percentage
  - b. Need for blood transfusion will be recorded
  - c. Need for erythropoietin will be recorded
- f) Change from baseline to all post-treatment visits in urine microalbumin-to-creatinine ratio (UMCR) [Time Frame: Weeks 0, 2, 4, 12, 24, 36, 48]

Urinary Microalbumin and creatinine will be measured in each patient during each follow up

g) Change from baseline to all post-treatment visits in hemoglobin A1c [Time Frame: Weeks 0, 2, 4, 12, 24, 36, 48]

HbA1C will be measured in each patient during each follow up

h) Change from baseline to all post-treatment visits in random blood sugar (RBS) [Time Frame: Weeks 0, 2, 4, 12, 24, 36, 48]

RBS will be measured in each patient during each follow up

i) Percentage of patients with hypoglycemia (defined as blood glucose < 55 mg/dL or 3.0 mmol/L) at all post-treatment visits [Time Frame: Weeks 0, 2, 4, 12, 24, 36, 48]

Patients will be asked if he or she had experienced any episode of hypoglycemia with clinical features of altered level of consciousness, sweating, nausea or vomiting with blood glucose < 55 mg/dL or 3.0 mmol/L

j) Change from baseline to all post-treatment visits in eGFR [Time Frame: Weeks 0, 2, 4, 12, 24, 36, 48]

eGFR will calculated using MDRD formula for each patient during each follow up

k) Change from baseline to all post-treatment visits in Anti-Hypertensive medication if there is any. [Time Frame: Weeks 0, 2, 4, 12, 24, 36, 48]

All anti hypertensive medicines with their doses will be recorded including any changes in each patient during each follow up

1) Change from baseline to all post-treatment visits in Hypoglycemic agent if there is any. [Time Frame: Weeks 0, 2, 4, 12, 24, 36, 48]

All hypoglycemic agents including their doses with any changes will be recorded for all diabetic patients during each follow up

m) Change from baseline to post-treatment visits in urine total protein-creatinine ratio (UPCR) [Time Frame: Weeks 0, 24, 48]

Urinary total protein and Creatinine ratio will be done in each patient during defined visit.

n) Change from baseline to post-treatment level of serum Alpha Feto Protein [Time Frame: Weeks 0, 24, 48]

Serum Alpha Feto protein will be measured as a tumour marker for Hepato-cellular carcinoma and also Tumour of Testis and Ovary.

o) Change from baseline to post-treatment level of serum CEA level [Time Frame: Weeks 0, 24, 48]

Serum CEA level will be measured as a tumour marker for Colo-rectal Carcinoma and also for Cancer of Stomach, pancreas, breast, lungs, thyroid and ovary.

p) Change from baseline to post-treatment level of serum CA 19.9 level [Time Frame: Weeks 0, 24, 48]

Serum C.A 19.9 level will be measured as a tumour marker for Pancreatic Carcinoma

- q) Change from baseline to post-treatment level LDH level [Time Frame: Weeks 0, 24, 48]

  Serum LDH level will be measured as tumour marker for Lymphoma
- r) Change from baseline to post-treatment level of Beta 2 Microglobulin level [Time Frame: Weeks 0, 24,48]

Serum Beta 2 Microglobulin level will be measured as a prognostic tool, as CKD patients invariably has a raised serum level.

s) Change from baseline to post-treatment level of serum CA 125 level (in case of female patients) [Time Frame: Weeks 0, 24, 48]

Serum C.A 125 level will be measured as a tumour marker for Ovarian Cancer

t) Change from baseline to post-treatment level of PSA level (in case of male patients) [Time Frame: Weeks 0, 24,48]

Serum PSA level will be measured as a tumour marker for Prostatic Cancer.

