#### 4.8 Eligibility criteria

#### 4.8.1 Inclusion criteria

A patient is eligible for the study if all of the followings apply:

- a) Aged 18-80 years (inclusive)
- b) With chronic kidney disease (CKD)stage 3 to 5 (eGFR 60 to 0 mL/min/1.73m2 (inclusive)) Note: eGFR = estimated glomerular filtration rate
- c) Having provided informed written consent.

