#### Serious adverse events (SAEs)

- i) Anaphylaxis (Immediate)
- ii) Pulmonary embolism or infarction (Immediate)
- iii) Outset of any neoplastic change (Late)
- iv) Outset of new Cardiovascular events (Late)
- v) Outset of new Cerebrovascular or neurological events (Late)
- vi) Reactivation of treated tuberculosis (Late)
- b) Change from baseline to 24 week visit in estimated glomerular filtration rate (eGFR) and split renal function in all patients for Phase II [Time Frame: Weeks 0, 24]
  - eGFR with split renal function will be evaluated using DTPA Renogram.
- c) Change from baseline to 24 week visit in estimated glomerular filtration rate (eGFR) with serum creatinine level in patients with CKD 4 and below for Phase II [Time Frame: Weeks 0, 2, 4, 12, 24]
  - eGFR will be calculated by Serum Creatinine level using MRDR formula during all visits.
- d) Change from baseline to 24 week visit in need for dialysis in patients with CKD 5 for phase II [Time Frame: Weeks 0, 2, 4, 12, 24]

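### Secondary outcome (j) computes MDRD eGFR in every patient at every visit with no rule for dialysis visits or for which creatinine to use; primary (c) is exposed only if a CKD 3-4 patient starts dialysis

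*Combined protocol and SAP*

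**What the plan says.** Section 4.11.2 (j) is worded as "Change from baseline to all post-treatment visits in eGFR", at weeks 0, 2, 4, 12, 24, 36 and 48, with the instruction that "eGFR will calculated using MDRD formula for each patient during each follow up". No patients are set apart.

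Patients on dialysis fall within this. Section 4.8.1 admits CKD stages 3 to 5 down to an eGFR of 0, none of the 15 exclusions in 4.8.2 concerns dialysis, and the need-for-dialysis scale in 4.11.1 runs from 0 (none) to 7 (three times a week). Questionnaire 1 in Annexure C carries that scale and is completed at all visits.

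On serum creatinine, 4.11.2 (c) adds: "In case of patients having dialysis Pre and Post dialysis S. Creatinine levels will be measured at or near follow up dates". Each investigation form in Annexure D has one creatinine line and one eGFR line.

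The kidney-function primaries in 4.11.1 are split as follows:
- (b), all patients, weeks 0 and 24: "eGFR with split renal function will be evaluated using DTPA Renogram". The week-48 form lists the renogram as well.
- (c), change in creatinine-based eGFR to week 24 "in patients with CKD 4 and below for Phase II", with the instruction that "eGFR will be calculated by Serum Creatinine level using MRDR formula during all visits" (MRDR is presumably MDRD).
- (d), change to week 24 in "need for dialysis in patients with CKD 5 for phase II".

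The analysis section, 4.15, has no rule for dialysis visits, for missing values, or for a patient who starts dialysis during follow-up.

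**The concern.** A creatinine formula reads kidney function from how much creatinine stays in the blood. Once dialysis is also removing it, the result no longer describes the patient's own kidneys. Followed as written, (j) mixes such values with valid ones and takes a change from baseline across them. Two creatinine values are collected at a dialysis visit, and whoever fills in the single line on the form decides which one counts.

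Every patient receives the cell treatment (4.2, 4.9) and there is no untreated arm, so change from baseline is the main evidence on whether progression is limited or reversed (3.2 iii). With 31 patients planned, a few distorted values can move a mean. Outcomes can also contradict each other: a patient who stops dialysis is a success under primary (d) but can read as a decline under (j).

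Primary (c) has a narrower form of the problem. If a CKD 3-4 patient starts dialysis before week 24, the eGFR fall can be partly masked. Outcome (d) is worded for CKD 5 and the plan does not say whether stage is fixed at baseline, so it is unclear whether that start is counted anywhere.

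**Working it through.** The plan gives no figure on this point. Its sample size reproduces (7.849 / 0.250 = 31.4, stated as 31) but plays no part in what follows.

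**Inputs, all assumed and none in the documents.** Post-dialysis creatinine is a fraction f = 0.5 to 0.7 of the pre-dialysis value. eGFR varies as creatinine to the power -k, with k = 1.0 to 1.2. The GFR values and patient counts below are illustrations.

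**Factor.** A post-dialysis sample multiplies the pre-dialysis eGFR by g = f^-k:
- f = 0.7: 1.429 (k = 1.0), 1.534 (k = 1.2)
- f = 0.5: 2.000 (k = 1.0), 2.297 (k = 1.2)

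The post-dialysis range is thus 1.43 to 2.30. Taking the pre-dialysis value as true sets g = 1 for that sample, so the unspecified sample spans 1.0 to 2.30. Any bias in the pre-dialysis value itself is not quantified here.

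**One patient, change read by the formula (mL/min/1.73 m2):**

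| Case | True change | Pre-dialysis sample (g = 1) | Post-dialysis sample |
|---|---|---|---|
| (j), dialysis starts, GFR stays 8: 8g - 8 | 0 | 0 | +3.4 to +10.4 |
| (j), dialysis stops, GFR stays 8: 8 - 8g | 0 | 0 | -3.4 to -10.4 |
| (j), dialysed throughout, same g, GFR 8 to 6: -2g | -2 | -2 | -2.9 to -4.6 |
| Primary (c), dialysis starts, GFR 18 to 10: 10g - 18 | -8 | -8 | -3.7 to +5.0 |

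A patient who stays on dialysis at GFR 8 but whose sample switches from pre- to post-dialysis also reads +3.4 to +10.4. The reverse switch reads -3.4 to -10.4.

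In the primary (c) case the result reads as improvement only if 10g > 18, that is, if f < (10/18)^(1/k) = 0.556 (k = 1.0) or 0.613 (k = 1.2).

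**Mean of primary (c), two of 20 patients start dialysis as above, the rest unchanged.** True mean: 2 x (-8) / 20 = -0.8.
- Leaving the two in shifts the mean by 2 x 10(g - 1) / 20 = g - 1: 0 with the pre-dialysis sample, 0.43 to 0.53 at f = 0.7, and 1.00 to 1.30 at f = 0.5.
- Dropping the two gives a mean of 0, a shift of +0.8.

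The two options break even at g = 1.8. Which is worse depends on the sample, so silently dropping dialysis visits is not a neutral repair.

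**The case against.** The plan already separates its kidney outcomes sensibly. DTPA GFR, which does not use creatinine, is primary in all patients at weeks 0 and 24. Creatinine eGFR is primary only in the earlier stages, and dialysis need is the outcome in CKD 5. The dialysis score at every visit makes the affected visits identifiable. Outcome (j) is one of 20 secondary outcomes. If the pre-dialysis sample were always used and taken as true, the start and stop errors above would be zero. The GFR values and the two-of-20 example are invented.

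Most of this stands, and it limits the weight of the point. It does not close the gap. Nothing in the plan lets DTPA GFR replace the MDRD value, and DTPA is not done at weeks 2, 4, 12 or 36. No rule uses the score in (c) or (j). The plan does not choose the pre-dialysis sample, and the validity of that sample in a dialysed patient is itself only assumed.

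Two stronger readings are tempting and are not supported. A reader might infer that the rule flatters the treatment. It does not do so consistently: the error is upward when dialysis starts and downward when it stops, and it can vanish or exaggerate a decline in patients dialysed throughout. A reader might also infer that primary (c) is biased as it stands. It is affected only if a CKD 3-4 patient starts dialysis by week 24, and the documents give no rate for that.

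**Conclusion.** The gap in (j) is real. The written rule takes in visits at which the formula does not measure native kidney function, and neither (j) nor secondary (c) says which of the two collected creatinine values is used. A change from baseline can be created or hidden by dialysis history or by a switch of sample, in either direction.

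The size depends on the sample: a factor of 1.43 to 2.30 for post-dialysis relative to pre-dialysis, or 1.0 to 2.30 for the unspecified sample if the pre-dialysis value is taken as true. These figures rest wholly on the assumed inputs; the gap itself does not.

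The effect on primary (c) is conditional and of unknown size, and DTPA GFR limits the damage at week 24. This should be fixed before analysis, but it ranks no higher than that.

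**What to change.** 1. **Secondary (j).** Report MDRD eGFR change only where the need-for-dialysis score is 0 at both baseline and the visit, with the n at each visit. Always show beside it, by visit, the number who were off dialysis at baseline and have since started, counted as progression, so that the exclusion does not hide deterioration. Describe patients on dialysis by the score and by the DTPA GFR already planned at weeks 0, 24 and 48. Patients on dialysis at baseline have no change value in (j), including those who later stop.
2. **Secondary (c).** For patients on dialysis, compare pre-dialysis with pre-dialysis and post-dialysis with post-dialysis creatinine, and report them separately from patients not on dialysis.
3. **Primary (c).** Fix CKD stage at baseline. State that the mean change is in patients not on dialysis at week 24, and give its n. Report beside it, as progression, the number of baseline CKD 3-4 patients who started dialysis by week 24, with their week-24 DTPA GFR where available. Report deaths too if they are recorded. A sensitivity analysis ranking these patients worst is optional.

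**Cost.** The change is to outcome and analysis wording, with no new tests or visits. Because the forms have a single creatinine line, values from dialysis patients must be labelled pre or post. Fewer patient-visits contribute to (j) and primary (c), and the remaining mean is conditional on being off dialysis, so it must always be read with the progression count.

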#### 4.8.2 Exclusion criteria

Any patient meeting any of the exclusion criteria will be excluded from study participation.

- 1) Known hypersensitivity to any component used in the study.
- 2) With inadequate hematologic function with: absolute neutrophil count (ANC) <1,500/μL OR platelets < 100,000/μL OR Hemoglobin < 8 g/dL
- 3) With impaired hepatic function with: serum bilirubin, aspartate aminotransferase (AST), alanine aminotransferase (ALT) or alkaline phosphatase (AKP), prothrombin time above and normal reference and serum albumin below normal reference range.
- 4) With hemoglobin A1c (HbA1c) > 8.0%
- 5) With serious prior or ongoing medical conditions (e.g. concomitant illness such as cardiovascular (e.g. New York Heart Association grade III or IV), hepatic e.g. Child-Pugh Class C), psychiatric condition, alcoholism, drug abuse), medical history, physical findings, ECG findings, or laboratory abnormality that in the investigators' opinion could interfere with the results of the trial or adversely effect the safety of the patient

- 6) Pregnant or lactating women or premenopausal with childbearing potential but not taking reliable contraceptive method(s) during the study period
- 7) With known history of human immunodeficiency virus (HIV) infection or any type of hepatitis
- 8) Judged to be not applicable to this study by investigator such as difficulty of followup observation
- 9) With any other serious diseases/medical history considered by the investigator not in the condition to enter the trial
- 10) Known or suspected abuse of alcohol or narcotics
- 11) With known history of cancer within past 5 years
- 12) With any autoimmune disease
- 13) With congenital kidney disease
- 14) With precancerous condition or with raised tumour markers like Alpha feto protein, Carcino embryonic antigen (CEA), C.A 19.9, C.A 125, Serum PSA above normal reference range.
- 15) Participants having a harvested total "Adipose Derived Stem Cell (ADSC)" count (in 5 ml SVF solution) less than 1 x 10^6 will be excluded from the study.

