#### 4.15 Data analysis

The edited data will then be entered on to the template of SPSS® 16 and STATA® 10/IC.

For Back ground variables and socio-demographic data descriptive statistics and relative frequency (percentage) will be generated.

Through univariate analysis the base line characteristics and treatment outcome will be compared. The effect of treatment will be identified through Multivariate analysis after adjusting for possible confounders. Relative risk with 95% CI will be generated through binary logistic regression adjusting for all possible confounders.

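### Five tumour markers required to be within range at entry are defined only as change from baseline, so one patient's rise above the limit need never be reported

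*Combined protocol and SAP*

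**What the plan says.** **Entry.** Exclusion 14 (section 4.8.2) removes patients with "raised tumour markers like Alpha feto protein, Carcino embryonic antigen (CEA), C.A 19.9, C.A 125, Serum PSA above normal reference range".

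**Outcome.** In section 4.11.2, items (n) AFP, (o) CEA, (p) CA 19.9, (s) CA 125 in women and (t) PSA in men are each described as a marker for named cancers and measured at weeks 0, 24 and 48. Each is defined only as a change, as in "Change from baseline to post-treatment level of serum Alpha Feto Protein". None has an upper limit, a count of patients who become abnormal, a shift table or a listing.

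**Two neighbouring items differ.** For (q) the protocol states: "Serum LDH level will be measured as tumour marker for Lymphoma". LDH is not named in exclusion 14. For (r) it states: "Serum Beta 2 Microglobulin level will be measured as a prognostic tool, as CKD patients invariably has a raised serum level".

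**Analysis.** For all outcomes, section 4.15 says "Through univariate analysis the base line characteristics and treatment outcome will be compared", followed by adjusted multivariable models. Section 4.16 plans tables, cross tables and charts.

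**Related outcomes.** New neoplastic change is item (iii) of the serious adverse events (SAEs) in the primary safety outcome (section 4.11.1, to week 48). No text ties a marker result to it. Secondary item (i) is built differently from the markers: "Percentage of patients with hypoglycemia (defined as blood glucose < 55 mg/dL or 3.0 mmol/L) at all post-treatment visits".

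**The concern.** A tumour marker measured after a cell therapy is there to pick up the odd patient whose value climbs. Nobody expects the whole group to shift. Since nobody may enter with one of the five named markers above range, every later value above the limit is a new crossing, and the natural summary is a count of patients.

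Change from baseline, summarised over about 31 people, answers another question: whether the average moved. A report could then say that a marker showed no significant change while one patient had a striking rise with no diagnosis by week 48. That is where the markers add to the SAE count, because a diagnosed cancer is already captured there.

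**Working it through.** **1. The plan's own figure.** Section 4.6 gives N = AB/C with A = 1.000, B = 7.849 and C = (0.5/1.0)² = 0.250. So N = 7.849/0.250 = 31.4, stated as about 31. This is a calculation for one mean change; nothing in it is specific to the markers. I use n = 31 below.

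**2. One riser among n patients.** Let the other n − 1 changes have mean 0 and standard deviation (SD) 1, and let one patient rise by k SD. Then:

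- mean change = k/n
- sample variance s² = k²/n + (n − 2)/(n − 1)
- t = (k/n)/(s/√n) = k/√(k² + n(n − 2)/(n − 1))

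For n = 31, n(n − 2)/(n − 1) = 31 × 29/30 = 29.97.

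| Rise k (SD) | Mean change k/31 | t | Two-sided p (30 df) |
|---|---|---|---|
| 5 | 0.16 | 5/√54.97 = 0.67 | 0.51 |
| 10 | 0.32 | 10/√129.97 = 0.88 | 0.39 |
| 20 | 0.65 | 20/√429.97 = 0.96 | 0.34 |
| no limit | – | tends to 1 | 0.33 |

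The riser inflates the SD as fast as the mean, so t stays below 1. As an illustration (assumed figures), a rise of 60 ng/mL with SD 1.5 is k = 40. The mean moves by 60/31 = 1.9 ng/mL, t = 40/√1629.97 = 0.99, and p = 0.33.

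**3. Simulation with random variation in the other 30 changes.** The t-test reached p < 0.05 in 3.8% of runs at 5 SD, 1.4% at 10 SD and 0% at 20 SD. A larger rise made significance less likely. The Wilcoxon test stayed at about 4 to 5%, its null rate, and the median moved about 0.04 SD.

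**4. Smaller denominators.** CA 125 and PSA each apply to one sex. With an assumed n = 15, the limiting p is again 0.33, and the simulated t-test rates were 3.0%, 0.1% and 0%.

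**5. What a count would show.** One patient above the limit in 31 is 1/31 = 3.2% (exact 95% CI 0.1% to 16.7%). None in 31 gives a one-sided 95% upper limit of 1 − 0.05^(1/31) = 9.2%.

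**6. Chance crossings.** Assumptions, not in the documents: normally distributed values, upper limit at the 97.5th percentile, and visit-to-visit correlation ρ. Each patient has four markers (AFP, CEA, CA 19.9 and one of CA 125 or PSA) at two visits, so there are 31 × 4 × 2 = 248 values.

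| ρ | Chance of a value above the limit, given normal at entry | Expected in 248 |
|---|---|---|
| 0.5 | 0.021 | 5.2 |
| 0.7 | 0.017 | 4.3 |
| 0.9 | 0.011 | 2.6 |

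**The case against.** **The protocol defines a variable, not a test.** Section 4.15 names no mean, t-test or other summary for any marker, and individual values are recorded on the Annexure D forms at weeks 24 and 48. A reader might infer that a group t-test is planned; the documents do not say so. This stands, and the point is conditional on it. But the only comparison described is a group one, section 4.16 foresees no patient listing, and section 5 says individual data are not reported. Individual reporting therefore cannot be assumed.

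**A cancer would not be lost.** A reader might infer that a new neoplasm could be hidden. It could not be hidden by this choice: once diagnosed, it counts as SAE (iii) whatever the group mean of a marker. This also stands, and it limits the gap to a rise without a diagnosis.

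**Not every item is selected to be normal.** Items (n) to (t) are seven, and exclusion 14 names five of the markers. LDH is absent, although the word "like" may make the list illustrative, and beta-2 microglobulin is expected to be raised. Counting values above the limit for beta-2 microglobulin would flag nearly everyone. The point is confined to the five.

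**Counting has a price.** A few values will cross the limit by chance (step 6), and in a study of 31 patients they could be misread as cancer signals.

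**Selection bias does not add to the case.** A reader might infer that entry on normal values biases the mean change through regression to the mean. With the limit at the 97.5th percentile, the shift is (1 − ρ)φ(1.96)/0.975, or 0.03, 0.018 and 0.006 SD for ρ of 0.5, 0.7 and 0.9. It runs upwards, towards a false alarm, and so would not conceal a rise. The documents give no screening data that would support a larger figure.

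**Conclusion.** The point holds for AFP, CEA, CA 19.9, CA 125 and PSA. Patients enter with these not above range, the outcome is defined only as change, and no rule brings an individual crossing to the reader's attention. If the change is summarised by group, one patient's rise is practically invisible: p tends to about 0.33 at n = 31 whatever its size, and rank tests and medians do no better. This rests on a single riser and otherwise unsystematic changes. It needs no assumption about the size of the rise or the marker's units.

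The consequence is a possible unreported marker rise without a diagnosed cancer. The documents do not support the stronger readings that a group-mean test is prescribed, that a diagnosed cancer could be missed, or that all seven items start normal. This is a minor, inexpensive improvement to how secondary safety data are reported.

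**What to change.** - **AFP, CEA, CA 19.9, CA 125 and PSA.** Report the number and percentage of patients above the upper reference limit at week 24 and at week 48, using women only as the denominator for CA 125 and men only for PSA. This is the form already used for hypoglycaemia, and exclusion 14 supplies the cut-off.
- **Listing.** Add a de-identified listing, by study code, of every such value with its baseline, any repeat result and whether SAE (iii) was recorded. State that this is consistent with the confidentiality wording in section 5.
- **Mean change.** Keep it for these five markers as descriptive only.
- **LDH.** Use a shift table against baseline status, since exclusion 14 does not name it.
- **Beta-2 microglobulin.** Leave as change from baseline.
- **Interpretation.** Say in advance that a few isolated values above the limit are expected by chance (about 3 to 5 of 248 under the assumptions in step 6).

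The cost is one table type and one listing. The values are already collected under Annexure D, and neither the sample size nor the visit schedule changes. The downside is the handful of chance crossings, which the repeat-result column and the interpretive note help the reader to weigh.
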